We propose a randomized controlled trial to study the efficacy and safety of a 10-day tapering course of hydrocortisone treatment for infants <30 weeks estimated gestational age at birth who remain intubated at 14 - 28 days postnatal age. Based on previous Network data these criteria define a population with a risk of death or BPD at 36 weeks postmenstrual age of approximately 65 – 75%. The primary outcome for this study will incorporate both (1) survival without moderate to severe BPD by Network physiologic definition and (2) survival without moderate or severe NDI at 22 - 26 months corrected age. Therefore, the results of this study will be reported only when follow-up data are available unless (1) the trial is stopped early by the DSMC because of strong evidence of benefit or harm, or (2) at the time all subjects have completed treatment the DCC finds a substantial survival benefit favoring hydrocortisone ($p < 0.001$). Individual study assignment will remain masked until the follow-up is completed. Secondary outcomes will include short term measures such as respiratory morbidities and growth at 36 weeks postmenstrual age and long term measures including growth and other outcomes at 22 - 26 months corrected age.

STATEMENT OF THE PROBLEM

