preliminary evidence from a small cohort study that hydrocortisone is equally efficacious as dexamethasone in facilitating extubation in preterm infants. Therefore, we propose a randomized, masked, placebo-controlled trial to study (1) the efficacy of hydrocortisone in facilitating extubation and thereby increasing survival without moderate or severe BPD and (2) the safety of HC for this use, by assessing the effect of hydrocortisone on survival without moderate or severe NDI at 22 - 26months adjusted age.

METHODS/PROCEDURES

(1) Study design: Randomized, masked placebo-controlled trial.

(2) Study population: Patients eligible for this study will be infants between 14 – 28 postnatal days who:

- (a) are <30 weeks estimated gestational age, to be randomized in two strata: $\leq 26^6$ and $27^0 - 29^6$ weeks);
- (b) were inborn at an NRN site or were admitted to an NRN site ≤ 72 hours postnatal age;
- (c) have received ≥ 7 days of mechanical ventilation;
- (d) are receiving mechanical ventilation through an endotracheal tube .

This population is at very high risk for death or moderate to severe BPD, based on previous NRN data (approximately 65 – 75%, see data below), and is a population for whom the most recent Cochrane review suggests it is reasonable to consider corticosteroid therapy (9). Deferring study entry until 14 days postnatal age will avoid the period of highest risk for spontaneous intestinal perforation (34).

Data provided by [name] for the two year period 2006 – 2007, using the physiologic definition of moderate to severe BPD, i.e., supplemental oxygen and/or positive pressure ventilation at 36 weeks postmenstrual age showed that:

Of infants who received ≥ 7 days of mechanical ventilation in the first 14 days, the percentage surviving without BPD was:

401-999g BW: 368/1482 (24.83%)
1000-1500 BW: 166/399 (41.80%)
Total (401-1500 BW): 534/1881 (28.4%)

Of infants who received ≥ 7 days of ventilation in the first 28 days, the percentage surviving without BPD was:

401-999g BW: 457/1528 (29.91%)
1000-1500 BW: 229/490 (46.73%)
Total (401-1500 BW): 686/2018 (33.99%)

Of infants who received ≥ 14 days of ventilation in the first 28 days, the percentage surviving without BPD was:

401-999g BW: 292/1249 (23.38%)
1000-1500 BW: 57/222 (25.68%)
Total (401-1500 BW): 349/1471 (23.73%)

In addition, unpublished data from the SUPPORT trial showed that of the 526 infants who were on mechanical ventilation at 14 days, 372 (71%) died or developed BPD.

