(a) Respiratory support: Each center currently cares for these infants with techniques they feel appropriate, whether CPAP, CPAP with IMV, high-flow nasal cannula or other. This study will not prescribe the technique to be used. Because this is an RCT and because enrollment will be stratified by center and study treatment will be masked, the center-specific and attending-specific techniques should be balanced in both treatment groups equally over the course of the trial and therefore not introduce bias.

(b) Open-label glucocorticoid therapy

(i) Infants who remain successfully extubated are not to be treated with open-label glucocorticoids as therapy for BPD. This will be a protocol violation.

(ii) Infants who are not extubated during the study treatment period or who are subsequently re-intubated may be treated with open-label dexamethasone after ≥ 4 days following the last dose of study drug. Open-label dexamethasone will be encouraged to be prescribed as described by Doyle (15). Further treatment with HC for prevention/treatment of BPD will be considered a protocol violation. The rationale for this plan is as follows: (1) HC has not been demonstrated in an RCT to be efficacious for extubation, whereas dexamethasone has (8, 9, 15); (2) this design will permit a true RCT of HC without open-label contamination of the placebo group. At the same time, we will not be denying treatment to the group of infants that meta-analysis suggests derive net benefit from treatment with dexamethasone (13)

(6) Definition of successful extubation: An infant who remains extubated for at least one week, including at least 3 days (72 hours) after the last dose of study medication, will be considered to be successfully extubated in response to this treatment.

(7) Laboratory specimens: none

(8) Analysis of study outcomes

(a) Study specifications and definitions

(i). Analysis will be by intention to treat.

(ii) Moderate or severe BPD is defined as the need for supplemental oxygen by NRN physiologic definition at 36 weeks estimated gestational age. This includes an oxygen withdrawal test for infants receiving $<0.30\text{FiO}_2$, as described in the study manual of procedures. For this study, this determination will be made between 36⁰ to 36⁶ weeks.

(iii) Infants discharged on oxygen prior to 36 weeks gestation will be evaluated at 36 weeks gestational age at a follow-up clinic visit, a home visit or by telephone if necessary.

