(iv) Outcomes assessed at 22 - 26 months corrected age will be the standard NRN follow up assessments: demographics, medical history including neurosensory outcomes, physical and neurologic examination, neurodevelopmental and behavioral assessment following the NRN Follow-up protocol.

(v) “Severe neurodevelopmental impairment” will be defined as (1) a BSID-III cognitive score or BSID-III motor score more than 2 SD below the mean (<70); OR (2) a Gross Motor Function classification code of 4 – 5 (Level 2 or 3) indicating moderate to severe cerebral palsy; OR (3) severe to profound hearing impairment (no functional hearing with amplification); OR (4) bilateral blindness that cannot be corrected.

(vi) “Moderate neurodevelopmental impairment” will be defined as (1) BSID-III cognitive score or BSID-III motor score 1 – 2 SD below the mean (70 – 84); OR (2) a GMFCS code of 2 -3 (Possible Level 1 or Level 1) indicating no cerebral palsy or mild cerebral palsy; OR (3) moderate hearing impairment (can hear and follow directions with amplification);); OR (4) moderate vision impairment (limited vision with correction or unilateral blindness).

(vii) Because the primary outcome for this study includes evaluation at 22 - 26 months, earlier study outcomes will not be reported unless the DSMC stops the trial prematurely because of strong evidence of benefit or harm, or at the time all

subjects have completed treatment the DCC determines a substantial mortality benefit favoring hydrocortisone that is significant at $p < 0.001$.

(b) Primary outcome measure and analytic approach: The primary outcome for this study will include both a measure of efficacy (improvement in survival without physiologically defined moderate to severe BPD) and safety (survival without moderate or severe NDI at 22 - 26 months corrected age). Because the primary study outcome will not be known until evaluation of the outcomes at 22 - 26 months corrected age, BPD outcome data will not be released until after this time.

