As summarized in the subsections below, a sample size of 800 subjects will be adequate to provide the study with a power of 80% for the efficacy hypothesis and a probability of greater than 80% of a successful safety evaluation. With the population available (below), this sample size should allow completion of enrollment in less than 3 years, will give a clear answer regarding the efficacy of hydrocortisone for improving survival without moderate or severe BPD, and will allow a reasonable assessment of safety and potential benefit at 22 - 26 months corrected age.

(i) Efficacy:

Empirical studies of the effect of alternative analytic approaches for binary outcomes (e.g. tests of differences in proportions, logistic regression, Mantel-Haenszel tests, and Poisson regression models) indicate that unless the study has both substantial imbalance of sample sizes across strata and the substantial stratum-specific heterogeneity of treatment effect, power calculations for the various approaches can reasonably be approximated by standard tests for differences in proportions. Consequently, we used standard software to estimate sample sizes for a power of 0.80 under the assumption that the risk of death or BPD at 36 weeks on the control arm was in the range of 65% to 75% (or alternatively that the probability of survival without BPD was in the range of 25% to 35%). Considering a 10 percentage point difference in survival without BPD to be clinically significant, improving survival without BPD from approximately 25% in this population (historical NRN data) to 35% with a power of 0.80 would require a sample size of 658 infants. If the incidence of survival without BPD in the placebo group has improved over time to 35%, we can achieve a power of 0.80 to detect an increase to 45% with a sample size of 752. A sample size of 800 subjects will be adequate to assure that the study has a power of at least 80% to detect a 10 percentage point improvement in outcome regardless of the baseline incidence of survival without BPD, with a margin for a small loss in power if the treatment effect has modest heterogeneity across strata.

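### Section (8)(a)(ii) spells out moderate or severe BPD as oxygen need only, while section (2) spells out the same named definition as oxygen, positive pressure, or both; an infant on positive pressure in room air could be scored either way.

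*Combined protocol and SAP*

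**What the plan says.** Three parts of the combined protocol and SAP bear on this.

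- **Section (8)(a)(ii), the definition in the analysis section:** "Moderate or severe BPD is defined as the need for supplemental oxygen by NRN physiologic definition at 36 weeks estimated gestational age". The text continues "This includes an oxygen withdrawal test for infants receiving" less than 0.30 FiO2, and refers to the study manual of procedures. Positive pressure is not mentioned.
- **Section (2), Study population:** the 2006–2007 Network data were compiled "using the physiologic definition of moderate to severe BPD, i.e., supplemental oxygen and/or positive pressure ventilation at 36 weeks postmenstrual age".
- **Section (5)(a), support after extubation:** left to each center, "whether CPAP, CPAP with IMV, high-flow nasal cannula or other".

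Elsewhere the outcome is named without being spelled out. The opening summary has "survival without moderate to severe BPD by Network physiologic definition", and section (8)(b) has "improvement in survival without physiologically defined moderate to severe BPD". No section says how an infant on ventilation, CPAP or high-flow cannula in room air at 36 weeks is to be scored.

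**The concern.** An efficacy endpoint must put every infant in one category by a rule fixed before the arms are compared. Here the rule is spelled out twice, and the versions part company for one group: infants alive at 36 weeks on positive pressure who do not need supplemental oxygen.

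That group is close to where the treatment is expected to act. The aim is to facilitate extubation, and extubated infants move to whatever non-invasive support the center uses. Hydrocortisone could therefore change how many infants are in this group.

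Three decisions rest on the endpoint:

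- The efficacy test decides whether the safety evaluation is reached (section (8)(b)).
- The gain in survival without BPD is the numerator of the benefit-to-risk ratio that must exceed 4 (sections (8)(b) and (8)(c)(ii)).
- Conditional power for the primary outcome is computed at about 50% and 75% of 36-week evaluations (Possible problems, item (1)).

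**Working it through.** **1. The two definitions side by side, status at 36 weeks**

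| Infant | (8)(a)(ii), read literally | Section (2) |
|---|---|---|
| Died | Event | Event |
| Needs supplemental oxygen, with or without pressure | Event | Event |
| Positive pressure, no supplemental oxygen | Could be scored BPD-free | Event |
| High-flow cannula, no supplemental oxygen | Could be scored BPD-free | Not stated whether this is positive pressure |
| Neither oxygen nor pressure | BPD-free | BPD-free |

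The text around (8)(a)(ii) does not settle the third row. The only test it names is withdrawal of oxygen, which does not apply to an infant in room air. Item (iii) arranges a 36-week evaluation for infants sent home on oxygen and is silent on pressure support.

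**2. Size and direction of any bias**

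Let a_C and a_H be the proportions of all randomized infants in the disputed group on placebo and hydrocortisone. In each arm:

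success (oxygen only) = success (section (2)) + a

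so the risk difference changes by a_H − a_C. If infants move from ventilation with oxygen to CPAP in room air, a_H rises and benefit is overstated. If treatment lets infants come off all support, a_H falls and benefit is understated. The documents give neither proportion, so the sign is open.

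Each point of a_H − a_C also moves the increase in death/NDI tolerated at the point estimate by 1/4 = 0.25 point. This is the same arithmetic as the plan's example (10 points of benefit, 10/4 = 2.5).

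**3. The plan's sample size**

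Inputs from section (8)(c)(i): "improving survival without BPD from approximately 25% in this population (historical NRN data) to 35% with a power of 0.80" needs 658; 35% to 45% needs 752; 800 are planned. Allocation is 1:1 (section (4)(b)). The efficacy alpha is not stated; two-sided 0.05 without continuity correction is assumed because it returns both figures exactly.

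n per arm = [1.960·√(2p̄(1−p̄)) + 0.842·√(p₁(1−p₁) + p₂(1−p₂))]² / (p₂−p₁)²

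- 25% vs 35%: [1.960·√0.42 + 0.842·√0.415]² / 0.01 = 328.5, so 329 per arm, total **658**.
- 35% vs 45%: [1.960·√0.48 + 0.842·√0.475]² / 0.01 = 375.6, so 376 per arm, total **752**.
- Power at 400 per arm: 0.871 and 0.824.

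The section (2) data were compiled under the definition that includes positive pressure (for example 349/1471 = 23.7%). If (8)(a)(ii) is brought into line with section (2), no planning figure moves.

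**4. If the oxygen-only reading were applied (assumptions, not document figures)**

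(a) The baseline shifts but the 10-point difference holds: for the baselines tried from 25% to 50%, required N is at most 784 and power at 800 is at least 0.809.

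(b) The same share f of death/BPD events in both arms is rescored as BPD-free. Success becomes 1 − (1−p)(1−f), so the difference shrinks to 0.10·(1−f):

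| f | From 25% vs 35% | Power at 800 | From 35% vs 45% | Power at 800 |
|---|---|---|---|---|
| 2% | 26.5% vs 36.3% | 0.849 | 36.3% vs 46.1% | 0.805 |
| 5% | 28.75% vs 38.25% | 0.814 | 38.25% vs 47.75% | 0.776 |
| 10% | 32.5% vs 41.5% | 0.752 | 41.5% vs 50.5% | 0.724 |
| 15% | 36.25% vs 44.75% | 0.688 | 44.75% vs 53.25% | 0.672 |

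Scenario (b) dilutes a true effect. A scenario with a_H above a_C would do the opposite. Nothing in the documents selects between them.

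**The case against.** The strongest reply is that there is only one definition. The sentence in (8)(a)(ii) is qualified by the Network physiologic definition, the opening summary and section (8)(b) invoke the same definition, and section (2) says what it contains. On that reading (8)(a)(ii) is an abbreviation, and sites following the Network's usual rule would score room-air positive pressure as BPD. The manual of procedures, which is not among the documents, may also settle the matter.

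Much of this stands. A reader might infer from the literal wording that pressure-supported infants in room air *will* be counted as successes. The documents do not establish that; they show only that they *could* be. But the qualifier does not remove the conflict. The sentence names the definition and then gives its content as oxygen need, and the manual is cited only for the withdrawal test.

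A second reply is that masking and stratification by center balance the support techniques between arms, as section (5)(a) argues. That is fair for center practice. It does not cover a difference produced by the treatment itself, though such a difference is a possibility and not a documented fact.

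A reader might also infer that the wording invalidates the sample size or builds in a bias toward hydrocortisone. Neither is supported: the planning figures hold once the definitions agree, and the sign of any bias is undetermined.

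**Conclusion.** The efficacy endpoint is defined inconsistently, and the inconsistency is more than missing detail: a stated rule in the analysis section conflicts with the plan's own description of the same definition, for infants whose number the treatment may affect. Under the literal reading the risk difference would be off by a_H − a_C, and the documents allow neither its size nor its sign to be found.

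This is not a sample-size error: 658, 752 and 800 stand. The power figures below 0.80 in the working arise only if the oxygen-only reading is applied and a large enough assumed share of events is rescored. They show sensitivity and are not a finding about this trial.

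The conclusion rests on the two passages alone. The manual could show that practice already follows section (2), in which case the correction is to wording only. It is still needed, because this endpoint governs the efficacy test, the route to the safety evaluation and the futility reviews.

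**What to change.** Reword (8)(a)(ii) to agree with section (2):

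- Moderate or severe BPD is supplemental oxygen (confirmed by the withdrawal test where it applies), positive pressure support, or both, at 36 weeks postmenstrual age.
- An infant on positive pressure without supplemental oxygen counts as having BPD.
- State how high-flow cannula in room air is classified, which neither section does now.
- Use postmenstrual age throughout. Section (8)(a)(ii) says estimated gestational age, whereas section (2) uses postmenstrual age.

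Confirm that the type of respiratory support at 36 weeks is recorded for every infant, including those discharged earlier, and that the manual carries the same rule. The documents mention days on positive pressure and standard Network measures at 36 weeks, but do not say outright that support type at that time is captured.

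The cost is a sentence or two of text and a check of the forms. N does not change. The wording should be settled before any comparison of 36-week outcomes by arm, including the futility reviews.

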This study will provide a sequential evaluation of the composite hypothesis that (i) administration of hydrocortisone has efficacy benefit in that it reduces the risk of death or BPD at 36 weeks; and (ii) administration of hydrocortisone has an acceptable long-term safety profile with respect to death or NDI at 22-26 months. Specifically, the primary outcome for this study will include both a measure of efficacy (improvement in survival without BPD) and safety (survival without major NDI at 22 - 26 months corrected age). This composite hypothesis will be evaluated sequentially. First, point and interval estimates of the adjusted relative risk obtained from a robust Poisson regression model controlling for center and gestational age will be used to test the hypothesis that infants treated with hydrocortisone had a lower risk of death or BPD at 36 weeks than infants treated with placebo. If this test of efficacy indicates benefit of the hydrocortisone arm then the safety of the treatment will be evaluated descriptively through an assessment of the risk to benefit ratio of the hydrocortisone treatment. Specifically, this safety outcome will be considered a “success” if either (1) the point estimate of risk of death/NDI is lower on the hydrocortisone arm than on the control arm, or (2) there is an increase in risk on the hydrocortisone arm, but the lower limit of a one-sided 95% confidence interval for the ratio of increased benefit for BPD to increased risk for NDI is greater than 4. In other words, for every additional 4 infants surviving without BPD, no more than 1 additional infant would experience death/NDI.

(c) Power calculations and sample size:

Consistent with the approach for evaluating the composite hypothesis defined above, the sample size calculations were conducted in two stages. First, standard power

analysis software was used to assess the sample size required to demonstrate a difference in death or BPD at 36 weeks on the two treatment arms. Second, simulation analyses were used to assess the probability of success for the safety outcome based on either of the two criteria defined above. The empirical probability of success for the descriptive analyses used to evaluate the safety outcome is analogous to the power of a formal hypothesis test.

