(ii) Safety: In view of the previous data suggesting possible benefit from hydrocortisone treatment, we anticipate that hydrocortisone treatment will be associated with improved survival without moderate or severe neurodevelopmental impairment (defined “NDI”) in this population. However, we do not anticipate demonstrating a statistically significant benefit with this sample size. Instead, we postulate based on previous data that hydrocortisone will provide a 3% improvement in survival without NDI (19,20), and will consider this outcome successful if either (1) the risk of death/NDI is lower on the hydrocortisone arm than on the control arm, or (2) there is an increase in

death/NDI in the hydrocortisone arm, but the lower limit of a one-sided 95% confidence interval for the ratio of increased benefit for BPD to increased risk for NDI is greater than 4. In other words, for every additional 4 infants surviving without moderate or severe BPD, we would have 95% confidence that no more than 1 additional infant would experience death/NDI. For example, if we achieve the successful outcome of an increase of 10% in survival without moderate or severe BPD, we would hypothesize also achieving an increase of 3% in survival without NDI, but would only define the treatment as a success if there were no more than a 2.5% increase in death or NDI in the treatment arm. There are no existing standards for this balance of joint outcomes; however, this design will allow us to evaluate efficacy within a reasonable boundary of safety.

Conceptually, the power associated with the safety component of the composite test is the probability of achieving one of the two criteria defined above. To evaluate this probability, we simulated study outcomes for 10,000 studies with sample sizes in the range of 350 to 400 subjects per treatment arm. The prevalence of survival without BPD was assumed to be 25% to 35% on the control arm with the hydrocortisone arm providing an improvement of 10%. The probability of survival without NDI on the control arm was assumed to be 42% based on available NRN data with an assumed improvement of 1% to 3% on the hydrocortisone arm based on data available from the literature. The correlation between death or BPD at 36 weeks and death or NDI at 18 to 22 months was assumed to be in the range of 0.4 to 0.5 based on available data from the NRN GDB.

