The results indicate that if the improvement in the death or NDI outcome is only 1% on the hydrocortisone arm, then the probability of achieving a “success” on the safety outcome is 0.68 to 0.71 if success requires the lower limit of a 95% confidence interval on the risk benefit ratio to exceed 4, but 0.80 to 0.81 if we only require that the point estimate achieve 4. However, if the true benefit of the hydrocortisone treatment on death or NDI is at least 3% then the probability of achieving a “success” on the safety outcome is 0.83 to 0.86 if success requires the lower limit of a 95% confidence interval on the risk benefit ratio to exceed 4, and 0.90 to 0.93 if we only require that the point estimate achieve 4.

(d) Secondary outcomes and analysis: After analysis of unadjusted risk differences, other factors known to affect neurodevelopmental outcomes (such as gender, maternal education and dexamethasone exposure) will be entered into a multivariable analysis of outcome using the robust Poisson regression models described for the primary efficacy outcome for each of the binary secondary outcomes defined below. Secondary outcomes will include:

(i) Standard NRN measures of morbidity and growth as collected for the GDB at 36 weeks postmenstrual age and at 22 - 26 months corrected age. We will include ROP incidence and severity as a secondary outcome of specific interest, as there has been conflicting information regarding the relationship of dexamethasone to

ROP. We will also include a questionnaire to assess breathing outcomes at 22 - 26 months of age using forms developed for the SUPPORT study.

(ii) Successful extubation during the intervention period.

(iii) Use of open-label dexamethasone

(iii) Respiratory status at 40 weeks estimated gestational age. Assessment of respiratory outcomes at this age has been reported to more accurately predict long term respiratory outcomes (personal communication [name]). This assessment will not include a room air challenge, as repeating the physiologic testing would be burdensome and the 40 week status is not the primary study outcome.

(e) Concomitant medications will be recorded, in particular diuretics, bronchodilators, antibiotics, iNO, caffeine and Vitamin A.

(f) Safety monitoring:

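### Should a gross motor code that may mean no cerebral palsy be enough, on its own, to count a surviving child as impaired in the safety outcome?

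*Combined protocol and SAP*

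**What the plan says.** Section (8)(a)(vi) of the combined protocol and SAP joins four criteria for moderate NDI by OR: a BSID-III cognitive or motor score of 70 to 84; a gross motor function code of 2 or 3; a hearing criterion; and a vision criterion. The motor codes are described as "Possible Level 1 or Level 1) indicating no cerebral palsy or mild cerebral palsy". Section (8)(a)(v) uses the same layout for severe NDI, where codes 4 and 5 are "Level 2 or 3) indicating moderate to severe cerebral palsy". Section (8)(a)(iv) refers the assessments to the network's own manual: "neurodevelopmental and behavioral assessment following the NRN Follow-up protocol".

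Moderate and severe NDI both count in the safety outcome. Under section (8)(b), safety is assessed descriptively once efficacy is shown. It succeeds if "the point estimate of risk of death/NDI is lower on the hydrocortisone arm than on the control arm", or, when the risk is higher, if "the lower limit of a one-sided 95% confidence interval for the ratio of increased benefit for BPD to increased risk for NDI" exceeds 4. Section (8)(c)(ii) illustrates the tolerance as "no more than a 2.5% increase in death or NDI in the treatment arm" against a 10-point gain in survival without BPD. The control rate of survival without NDI was "assumed to be 42% based on available NRN data".

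**The concern.** The codes, levels and meanings appear to run in parallel: code 2 is possible Level 1 and no cerebral palsy, code 3 is Level 1 and mild cerebral palsy. The text does not say that they pair in this way, but it is the natural reading. A child with both BSID-III scores at 85 or above, no hearing or vision criterion and code 2 is then counted with the dead and the impaired. The plan gives no reason, no frequency for this group and no analysis without it. It also does not say whether the 42% planning rate counted such children.

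At stake is the safety verdict. If code 2 is unrelated to treatment, counting it dilutes a true difference in death/NDI. That makes success slightly less likely under benefit and slightly more likely under harm. Because the rule turns on a sign or a cut-off, a few children could also decide the verdict in a single trial.

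**Working it through.** **Inputs from the plan.** Survival without NDI on control 42%, with a simulated improvement of 1 to 3 points; survival without BPD on control 25% to 35%, improved by 10 points; correlation 0.4 to 0.5; 350 to 400 per arm (all section (8)(c)(ii)). The budget expects 15% deaths and 90% follow-up. That gives 120 deaths and 0.90 × 680 = 612 children followed, so 732 evaluable, or 366 per arm.

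**Assumed.** f, the share of otherwise NDI-free survivors with code 2 alone: 2%, 5% or 10%, equal in both arms. The documents give no value. Central case: survival without BPD 30% v 40%, correlation 0.45.

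**Rule.** Let D_B and D_N be the differences (hydrocortisone minus control) in survival without BPD and without NDI. Success means D_N > 0, or [D_B − 1.645 × SE(D_B)] / (−D_N) > 4.

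**Reproducing the plan.** With f = 0, simulation over the plan's ranges gives 0.68 to 0.71 at a 1-point benefit and 0.83 to 0.86 at a 3-point benefit. The plan reports "0.68 to 0.71 if success requires the lower limit of a 95% confidence interval on the risk benefit ratio to exceed 4" and 0.83 to 0.86. The match needs the sampling error of D_N to be left out of the limit. With it included, the results are 0.59 to 0.60 and 0.78 to 0.80. That is a separate matter, but it shows which form lies behind the plan's figures.

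**Dilution.** If 42% excludes code 2, counting it multiplies D_N by (1 − f):
- 3-point benefit: 3 × 0.98, 0.95, 0.90 = 2.94, 2.85, 2.70 points.
- 2.5-point harm: 2.45, 2.38, 2.25 points.
- Code-2-only children on control: 0.42 × 366 × f = about 3, 8 or 15.

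**Check by hand at a 3-point benefit.**
- SE(D_B) = √[(0.30×0.70 + 0.40×0.60)/366] = 0.0351, so the average lower limit is 0.10 − 1.645 × 0.0351 = 0.0423. Divided by 4, it tolerates about 1.06 points of harm.
- SE(D_N) = √[(0.42×0.58 + 0.45×0.55)/366] = 0.0366. z = (0.030 + 0.0106)/0.0366 = 1.11, so the probability is about 0.87.
- At f = 10% the rates are 37.8% and 40.5%, and SE(D_N) = 0.0361. z = (0.027 + 0.0106)/0.0361 = 1.04, so about 0.85.

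This runs a little high because it holds the BPD limit at its average. The shift of about 1.5 points is the right order. The dilution of at most 0.3 points is small beside a standard error of 3.7 points.

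**Simulation, 400,000 trials per scenario, both definitions applied to the same trial.**

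| True effect on death/NDI | P(success), code 2 not counted | Counted, f = 2% / 5% / 10% | Verdicts differ |
|---|---|---|---|
| 3-point benefit | 0.840 | 0.838 / 0.833 / 0.827 | 3% / 5% / 8% |
| 2.5-point harm | 0.363 | 0.367 / 0.372 / 0.383 | 5% / 8% / 11% |
| 5-point harm | 0.167 | 0.172 / 0.180 / 0.195 | 3% / 5% / 8% |

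At a 1-point benefit the verdicts differ in 5%, 7% or 10% of trials.

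**If 42% already counts code 2.** The rate without it is 42/0.98, 42/0.95 or 42/0.90 = 42.9%, 44.2% or 46.7%. As written, success stays at 0.84 (3-point benefit) and 0.36 (2.5-point harm). Without code 2 it would be 0.843, 0.848 or 0.858, and 0.359, 0.352 or 0.341.

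**If code 2 depends on treatment.** Assume 5% on control and 3% or 8% on hydrocortisone, with a 2.5-point harm. The NDI-free rates become 42 × 0.95 = 39.9% against 39.5 × 0.97 = 38.3% or 39.5 × 0.92 = 36.3%. The harm reads 1.6 or 3.6 points, and success moves from 0.36 to 0.45 or 0.27.

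**The case for a change.** The strongest case for a change is that a small average effect can still decide one trial. Four children are 4/366 = 1.1 points, as much as the average tolerance worked out above. A choice of definition made after unblinding could not be shown to be independent of the result. The remedy would be cheap: confirm the intent, fix the wording and add one sensitivity analysis. Section (8)(b) also speaks once of major NDI, a term it does not define.

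The reading of the text stands, and so does the arithmetic. The inference to a defect does not:

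- No choice is left open. The codes are named and the criteria are joined explicitly, so an analyst would count code 2. Section (8)(c)(ii) defines NDI as moderate or severe, which settles the stray adjective.
- The criterion grades motor function and is not a diagnosis of cerebral palsy. A BSID-III score of 70 to 84 qualifies a child alone, with no cerebral palsy needed. A borderline motor grade fits that scheme, and the authors printed its meaning beside it.
- Opposite verdicts in some trials follow from the sharp success rule. Moving a BSID-III cut-off or a hearing category would have the same kind of effect.
- The larger shifts, to 0.45 or 0.27, come only from an assumed treatment effect on code 2. If that effect is real, it argues as much for keeping the code, because dropping it would make the safety outcome less sensitive.

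**Conclusion.** No change is needed. The plan does count code 2 alone as moderate NDI, but the documents do not show this to be an error, and what would settle the intent is in a follow-up protocol that is not part of them. With f between 2% and 10% and equal in both arms, the effect on the probability of safety success is about 2 points or less under a 3-point benefit or a 2.5-point harm, and just under 3 points under a 5-point harm. Those sizes rest on an assumed f and on the form of confidence limit that reproduces the plan's own figures. The efficacy test is untouched.

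Narrowing the criterion would be a trade-off with no demonstrated gain. It could remove a motor limitation that treatment affects, and it would put in doubt whether the 42% planning rate still applies. The sponsor may confirm the meaning of code 2 and the basis of the 42%, and may report code-2-only children by arm with the result excluding them. That is optional reporting from data already collected, and it needs no amendment.
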